6.1 Statistical Analysis

All analyses will be performed by intent to treat, and further evaluated per protocol. As a first step, we will assess distribution characteristics of the primary and secondary outcomes. Where appropriate, transformation of variables to combat skew or other irregularities will be employed. Participant characteristics will be summarized using means, medians, standard deviations, interquartile regions and ranges for continuous variables and sample counts and proportions generated for discrete characteristics. Comparability of treatment arms will be assessed on potentially confounding characteristics using tabular and graphical methods.

6.2 Outcome Variables

Below are the specific outcome variables planned for the study.

Primary Endpoints

Study feasibility is evaluated by several identified measures listed in §5.4, however others will be explored. Feasibility outcomes will be summarized using sample quantities and corresponding 80% confidence interval estimates. The specific thresholds that will determine study feasibility will be fully described in the manual of procedures.

Secondary Endpoints

Sleep quantity will be captured via a device that has polysomnographic capacity (e.g., Garmin Watch™), which continuously measures quantitative aspects of sleep (e.g., total sleep time, number of awakenings, wake time after sleep onset, etc.). The sleep diary that a participant logs their time in bed and time out of bed will help us correct any issues with the objective measures. The primary aspect of sleep quantity will be total sleep time, however others will be explored. Participants will be asked to wear the device all day and night during the study. Change in measures of sleep quantity will be calculated between baseline and midpoint, as well as baseline and final follow-up visit. The distribution of change in sleep quantity scores will be summarized using means and standard deviations or medians and interquartile ranges, as appropriate. We will develop 80% confidence interval estimates of inter- and intra- individual variation (i.e., standard deviation) of change in these measures.

Sleep quality will be measured by a validated self-report questionnaire: the Pittsburgh Sleep Quality Index (range: 0-21),³⁸ where higher scores indicate worse sleep. Change in sleep quality scores will be calculated between baseline and final follow-up visit. The distribution of change in sleep quality scores will be using means and standard deviations or medians and interquartile ranges, as appropriate. We will develop 80% confidence interval estimates of inter- and intra-individual variation (i.e., standard deviation) of change in these measures.

Biomarkers (i.e., melatonin, serotonin, cortisol, and inflammatory markers) will be measured by a reputable lab (e.g., University of Connecticut) utilizing commercially available quantitative immunoassays (ELISA). **Melatonin** will be estimated by measuring the major urinary metabolite of melatonin, 6-sulphatoxymelatonin. **Serotonin** production will be estimated by measuring the serum kynurenine/tryptophan ratio, which reflects the rate at which tryptophan is converted to kynurenine rather than serotonin.¹⁸ Therefore, lower rates of the kynurenine/tryptophan ratio indicate that more tryptophan is blunted towards the serotonin pathway. **Cortisol** will be estimated by measuring the urinary cortisol. **Serum inflammatory markers** (e.g., interleukins and tumor necrosis factor) will be estimated using a panel of several biomarkers, since inflammation is a heterogeneous/complex process.⁴³ These markers will be consolidated into one composite inflammatory score as previously described.⁴⁴⁻⁴⁶ Change in the biomarker measures will be calculated between baseline and final follow-up visit. The distribution of change in biomarker measures will be summarized using means and standard deviations or medians and interquartile ranges, as appropriate. We will develop 80% confidence interval estimates of inter- and intra- individual variation (i.e., standard deviation) of change in these measures.

Exploratory Outcomes

Sleep-related factors (i.e., mood, stress, and pain) will be measured. **Mood** will be evaluated by the validated questionnaire, the Center for Epidemiological Studies Depression scale^{39,40}, which measures severity of depressive symptoms (range: 0-60, with higher scores indicating more severe symptoms). **Stress** will be evaluated by the validated 14-item questionnaire, the Perceived Stress Scale⁴¹ (range: 0-56, with higher scores indicating more stress). **Pain** will be reported via a validated 24-item questionnaire, the Geriatric Pain Measure⁴² (range: 0-42, with higher scores indicating more pain). Change in measures of sleep-related factors will be calculated between baseline and final follow-up visit, as well as baseline and mid-point if data is available. The distribution of change in sleep-related factors will be summarized using means and standard deviations or medians and interquartile ranges, as appropriate. We will develop 80% confidence interval estimates of inter- and intra- individual variation (i.e., standard deviation) of change in these measures.

6.3 Statistical Methods

For both arms of the study, change over time will be calculated for each outcome variable and summarized using means and standard deviations or medians and interquartile ranges, as appropriate. For the majority of outcomes, week 1 and week 8 (i.e., visits that are before intake of the intervention products) will serve as the baseline assessment and those conducted at week 5 and week 12 (i.e., visits that are 4 weeks after intake of the intervention products) will serve as the follow-up assessment. However, due to the variable nature of sleep quantity we will collect several nights of data from 1 week before the intervention products are administered for baseline and during the last week of the intervention as follow-up. The median value during those weeks will be used to avoid skewing. Then the change between the 1-week estimated medians will be calculated. Additionally, change between baseline and midpoint (week 3 and week 10) will also be calculated and explored when data is available. The specific analyses for each aim are listed below.

Aim 1: Determine the feasibility of recruiting individuals for and implementing a tart cherry juice intervention in older adults with self-reported insomnia.

The aspects of feasibility that are indicated in §5.4 will be tabulated to determine feasibility. This is a descriptive analysis, thus no formal statistical methods will be employed. However pre-specified gradient thresholds that determine if each metric is feasible, in need of modification, or not feasible are documented in the Manual of Procedures.

Aim 2: Generate preliminary data for sleep quantity, sleep quality, and relevant biomarkers in older adults with self-reported insomnia enrolled in a double blind randomized placebo controlled tart cherry juice intervention.

The changes computed for the indicated measures as described in §6.2 will be averaged within each treatment arm (i.e., tart cherry juice vs placebo) and compared with a paired Student's t-test. A p-value less than 0.05 will be used to determine statistical significance.

Exploratory Aim: Explore the impact of tart cherry juice intake on sleep-related factors that may be impacted by the Aim 2 biomarkers in older adults.

The changes computed for the sleep related factors as described in §6.2 will be averaged within each treatment arm (i.e., tart cherry juice vs placebo) and compared with a paired Student's t-test. Additionally the changes in sleep related factors will be correlated (via Spearman Correlation) with change in biomarkers within each treatment arm (i.e., tart cherry juice vs placebo). A p-value less than 0.05 will be used to determine statistical significance.

CHAPTER 7 DATA MANAGEMENT AND QUALITY

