3.4 Number of Subjects and Study Duration

We aim to recruit a total of 20 individuals (both men and women) through local newspaper and internet advertisements, physician referrals, our registry of research volunteers, Hebrew SeniorLife (HSL) senior housing sites, and patient registries (e.g., HRC or Beth Israel Deaconess Medical Center). Given that a primary goal of this study is to determine recruitment and attrition rate, we may not have exactly 20 individuals who complete the study. Participants will remain in the study for a total of approximately 12 weeks.

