4.2 Recruitment Timeline and Randomization

Our trial proposes to enroll 20 individuals over approximately 6-months. In an attempt to account for the impact of order, we will randomly assign individuals to the order in which they receive the intervention and placebo. For example some individuals will start with the intervention and then placebo, others will start with the placebo and then the intervention. This process will be carried out while maintaining participant and investigator blinding. Block randomization will be employed as a means to reduce the impact of season/time.

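### The paired t-test on change scores for Aim 2 omits period, adds baseline noise and uses complete pairs only; a period- and baseline-adjusted cross-over model should replace it

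*Combined protocol and SAP*

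**What the plan says.** - **Test.** Section 6.3 (Aim 2) states that the changes "will be averaged within each treatment arm (i.e., tart cherry juice vs placebo) and compared with a paired Student's t-test", and adds: "A p-value less than 0.05 will be used to determine statistical significance". The Exploratory Aim uses the same test for mood, stress and pain.
- **Baselines.** In Section 6.3, "week 1 and week 8 (i.e., visits that are before intake of the intervention products) will serve as the baseline assessment", with follow-up at Weeks 5 and 12. For sleep quantity, one-week medians take the place of single visits. Each paired difference therefore uses four measurements.
- **Order and time.** Section 4.2 says that "we will randomly assign individuals to the order in which they receive the intervention and placebo", and that "Block randomization will be employed as a means to reduce the impact of season/time". Both are design measures. No period or sequence term appears in Section 6.3.
- **Population.** Section 6.1: "All analyses will be performed by intent to treat, and further evaluated per protocol".
- **Size and completion.** Section 3.4: "We aim to recruit a total of 20 individuals", but "we may not have exactly 20 individuals who complete the study". Section 4.4 retains the data of participants who withdraw. No section says how a participant with one period enters the paired test, and no imputation is planned.

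**The concern.** Three features of the test sit badly with a cross-over of 20 people.

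1. The participant already serves as their own control. Subtracting a separate baseline in each period brings in the noise of two more measurements, and it forces the baseline slope to be one when the data could estimate it.
2. The design treats order and season as worth controlling, but the analysis ignores them. Any period effect goes into the error term and, if completers are unequal across sequences, into the estimate.
3. A participant with one period has no pair and drops out of the test.

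The stakes are moderate. The 0.05 threshold is applied to every secondary outcome. Section 8.6 intends to judge preliminary efficacy from this study and to size later trials from the variation in change, so an inefficient contrast could carry over into the next design.

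**Working it through.** **Inputs.** The plan states no power, effect size, SD, correlation or dropout rate for Aim 2, so there is no figure of its own to reproduce. Assumed here: a two-sided test at 0.05 (sidedness is not stated), 1:1 allocation to sequence (not stated), equal variances s², correlation a between baseline and follow-up in the same period, and correlation b between any two measurements in different periods, with a ≥ b.

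**Step 1: variance of the contrast, large samples.**
- Difference of changes (as planned): 4s²(1−a).
- Difference of follow-ups alone: 2s²(1−b).
- Difference of follow-ups adjusted for the difference of baselines: 2s²(1−b)(1−r²), where r = (a−b)/(1−b).
- Because 1−a = (1−b)(1−r), planned/adjusted = 2/(1+r), which lies between 1 and 2.

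Under a correlation that decays with time over Weeks 1, 5, 8 and 12, this ratio is 1.45 to 1.84. Simply dropping the baselines is not a safe alternative. The ratio of planned to follow-up-only variance is 2(1−a)/(1−b), which is 2 × 0.2/0.5 = 0.80 at a = 0.8, b = 0.5, so there the change score is better.

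**Step 2: at n = 20.** Estimating the slope costs something. With two sequences of 10 and one covariate, the expected inflation of the adjusted variance is 1 + 1/(20−4) = 1.0625. The simulated columns use a period-adjusted ANCOVA on the paired differences and a true effect of 0.5 SD. Their simulation error is a few hundredths for the ratio and about one percentage point for power.

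| a / b | r | 2/(1+r) | ÷ 1.0625 | Simulated ratio | Power, planned | Power, adjusted |
|---|---|---|---|---|---|---|
| 0.6 / 0.6 | 0 | 2.00 | 1.88 | 1.86 | 39% | 62% |
| 0.7 / 0.6 | 0.25 | 1.60 | 1.51 | 1.54 | 50% | 66% |
| 0.8 / 0.6 | 0.50 | 1.33 | 1.25 | 1.26 | 66% | 75% |
| 0.9 / 0.6 | 0.75 | 1.14 | 1.08 | 1.08 | 92% | 93% |

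Check of the first row: the SD of the planned difference is √(4 × 0.4) = 1.265, so the noncentrality is 0.5/1.265 × √20 = 1.77, which gives about 39% on 19 degrees of freedom.

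**Step 3: period effect.** Let the paired difference have mean τ+π in one sequence and τ−π in the other. The paired t-test then estimates τ + π(n1−n2)/(n1+n2).
- Completers 10:10 give no bias; 11:9 gives 0.10π; 12:8 gives 0.20π; 10:6 gives 4/16 = 0.25π.
- At 10:6, a period effect of 0.4 SD shifts the estimate by 0.25 × 0.4 = 0.10 SD, so a true 0.50 becomes 0.40 (or 0.60 if the imbalance runs the other way).
- At 10:10, with π equal to 0.5 or 1.0 SD of the paired difference, type I error is 0.032 or 0.007. Power at τ = 0.66 SD of the paired difference falls from 0.80 to 0.72 or 0.49. The period-adjusted analysis stays near 0.05 and 0.80.

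**Step 4: one-period participants.** If 4 of 20 leave after the first period (assumed, two per sequence), the test uses 16. The complete-pairs variance exceeds that of an all-data model with a period term by 12.5%, 5% or 2.5% at between-period correlation 0, 0.6 or 0.8.

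**The case against.** The strongest reply is that feasibility is primary, Aim 2 is meant to generate preliminary data, and Section 8.6 leaves definitive efficacy to a later, adequately powered trial. With balanced completers the planned test is unbiased and errs on the cautious side. This stands, and it limits the severity.

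A reader might infer four stronger things that the documents do not support.

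- **That the variance is doubled.** Two is the large-sample ceiling, reached when a = b. Baseline and follow-up are four weeks apart within a period and the two follow-ups are seven weeks apart, so a > b is a reasonable expectation. At 0.9/0.6 the two analyses hardly differ.
- **That order biases the result.** Bias needs unequal completers, and the 10:6 split is extreme. If 4 of 20 leave at random from 10:10, the chance that all come from one sequence is 2 × C(10,4)/C(20,4) = 420/4845 = 8.7%, and the expected absolute leak is about 8% of the period effect. Dropout related to sequence could be worse, but nothing in the plan shows it.
- **That the dietary and medication restrictions starting at Week 0 make a period effect likely for all outcomes.** The argument fits mainly the sleep-quantity baseline, which covers that first week. The questionnaires and biomarkers are taken at Week 1, and certain sleep aids are stopped 2 to 3 weeks before a participant continues (Section 3.3).
- **That much information is discarded with one-period participants.** Step 4 shows a modest loss. The more serious points are possible selective dropout and the label. Section 6.1 may use intent to treat only to mean analysis regardless of compliance, and one-period data can still enter the by-arm summaries. Even so, the test itself omits those participants, and Section 4.4 allows withdrawal for low compliance, so exclusion may be related to the product.

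**Conclusion.** The concern holds as a point that should be fixed. The planned comparison is less precise than the design allows, does not account for period, and is a complete-pairs analysis under an intent-to-treat statement. The last point follows from the text alone. The loss of precision depends on correlations that the plan does not give: at n = 20 the variance ratio runs from about 1.86 down to 1.08 over the assumed settings, and the power gain from 23 percentage points down to 1, for an assumed 0.5 SD effect with equal variances and a ≥ b. The period effect is a matter of conservatism when completers are balanced, and of bias by the fraction |n1−n2|/(n1+n2) when they are not. The primary feasibility result does not depend on any of this.

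**What to change.** Before unblinding, amend Section 6.3 for Aim 2 and for the treatment comparison in the Exploratory Aim:

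- Make the main analysis a linear mixed model on end-of-period values (Week 5 and Week 12; the last-week summary for sleep quantity).
- Include treatment and period as fixed effects (sequence optional), a random participant effect, and the period baseline as covariate, split into the participant mean and the within-participant deviation. For completers, ANCOVA on paired differences with a period term is equivalent.
- Use small-sample degrees of freedom.
- Include every randomised participant with at least one follow-up value, and state how a participant with only one baseline is entered.
- Keep the paired t-test as a sensitivity analysis labelled complete pairs.

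The cost is a few error degrees of freedom, a few lines of code and an amended paragraph. No new data are needed.

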8.6 Potential Benefits

Participants may not receive any significant health benefit from participation, although some may benefit from knowledge of their health status, as well as potential therapeutic effects from the tart cherry juice. If our findings confirm that our intervention is feasible and demonstrates preliminary efficacy, subsequent trials will be appropriately designed using the variation in change in the outcomes gathered from this study. Such a study will be adequately powered to determine definitive efficacy of a dietary intervention to target biological pathways related to sleep quantity and quality.

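### Section 6.3 judges at least nine juice-placebo comparisons by unadjusted p<0.05 with no interval planned for the difference, and its within-arm correlations do not use the cross-over contrast

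*Combined protocol and SAP*

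**What the plan says.** Sections 3.5 and 5.4 make feasibility primary, sleep and biomarker outcomes secondary, and mood, stress and pain exploratory. For feasibility (Aim 1), Section 6.3 states: "This is a descriptive analysis, thus no formal statistical methods will be employed".

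For Aim 2, the average changes under juice and placebo are to be "compared with a paired Student's t-test". The exploratory outcomes are treated the same way. Under both aims Section 6.3 adds: "A p-value less than 0.05 will be used to determine statistical significance". Sections 6.1 to 6.3 give no multiplicity adjustment, no testing order and no statement that these p-values are descriptive. Within sleep quantity there is one named lead measure: "The primary aspect of sleep quantity will be total sleep time, however others will be explored".

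Under the Exploratory Aim, "the changes in sleep related factors will be correlated (via Spearman Correlation) with change in biomarkers within each treatment arm", again judged at 0.05.

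Section 6.2 plans 80% intervals for feasibility quantities. For the other outcomes the interval is for spread: "We will develop 80% confidence interval estimates of inter- and intra- individual variation (i.e., standard deviation) of change in these measures". No section plans an interval for the mean difference between juice and placebo.

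Section 8.6 looks ahead: "If our findings confirm that our intervention is feasible and demonstrates preliminary efficacy, subsequent trials will be appropriately designed". It adds that the later design will use the variation in change. It does not define preliminary efficacy. Section 3.4 aims for 20 participants and accepts that fewer may complete.

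**The concern.** The trial exists to supply preliminary data for a later study. A planner needs the size of the juice-placebo difference and its uncertainty. The plan's stated inference on that difference is a significance verdict, repeated over several outcomes. Some verdicts may be false leads, and a non-significant result in about 20 people says little. There is also an imbalance within the plan: the primary outcome is descriptive, while the outcomes ranked below it are declared significant or not.

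The correlations raise a different question. The Exploratory Aim concerns what juice does to mood, stress and pain through the biomarkers. Within one arm, two changes can move together over four weeks through placebo response, regression to the mean or period, with no juice effect at all. The cross-over gives each completer a juice-minus-placebo difference in every variable, and the planned correlations do not use it.

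**Working it through.** The documents state no number of tests, familywise error rate or power, so there is no figure of theirs to reproduce. Two-sided tests are assumed, because sidedness is not stated.

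**Count of tests (Sections 6.2 and 6.3)**
- Aim 2: total sleep time, PSQI, melatonin metabolite, kynurenine/tryptophan ratio, cortisol, inflammatory composite = 6.
- Exploratory: mood, stress, pain = 3. Juice-placebo comparisons: 6 + 3 = 9.
- Correlations: 3 factors × 4 biomarkers × 2 arms = 24. Total: 9 + 24 = 33.

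This is a minimum. Midpoint changes in sleep quantity, mood, stress and pain could add 4 (37 in all). Running everything in both the intent-to-treat and per-protocol sets (Section 6.1) would give 66 to 74. Further sleep measures are left open.

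**Chance findings if every null is true**
For k independent tests at 0.05, P(at least one) = 1 − 0.95^k and the expected number is 0.05k.

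| Family | k | P(at least one) | Expected |
|---|---|---|---|
| Aim 2 | 6 | 26.5% | 0.30 |
| All juice-placebo | 9 | 37.0% | 0.45 |
| Within-arm correlations | 24 | 70.8% | 1.20 |
| All | 33 | 81.6% | 1.65 |

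The outcomes share participants, so independence is only a reference case. In simulation under the global null (n = 20, common correlation assumed), P(at least one) for the nine comparisons was 38%, 34%, 27% and 21% at correlations of 0, 0.3, 0.5 and 0.7. For the six Aim 2 tests it was 27%, 25%, 21% and 17%. Correlation does not change the expected number.

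**What an interval would show**
The half-width for the mean paired difference is t/√n, in units of the SD of the differences.
- n = 20: 95%, 2.093/√20 = 0.47; 80%, 1.328/√20 = 0.30.
- n = 16 (an assumed number of completers): 0.53 and 0.34.

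At n = 20 an observed difference must therefore exceed 0.47 SD to reach p<0.05. If the true difference were 0.3 SD, a significant estimate in the right direction would be at least 0.47/0.3 = 1.56 times too large. As context only, power at n = 20 is 25% for 0.3 SD, and 80% power needs 0.66 SD.

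**Correlations and the period effect**
Let the two sequences be equal in size, d the period difference in change, s² the variance of change within an arm, and r the within-person correlation of the two changes.
- Within an arm, half the participants are in each period. Period variance relative to noise is (d²/4)/s².
- In juice-minus-placebo differences, period enters as +d or −d by sequence. The ratio is d²/[2s²(1 − r)].
- The second divided by the first is 2/(1 − r): 2 at r = 0 and 4 at r = 0.5.

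Unadjusted differences thus answer the better question but carry at least twice the relative period contamination when r ≥ 0. Centring the differences within each sequence removes it.

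**The case against.** This is a feasibility pilot, and much of the hierarchy one would ask for already exists. Feasibility is primary and descriptive, Aim 2 is framed as generating preliminary data, and mood, stress and pain are labelled exploratory. The inflammatory markers are collapsed into one score, and total sleep time leads sleep quantity. Formal familywise control would be out of proportion. The later trial is to be designed from the variation in change, for which intervals are planned, and definitive efficacy is left to that trial. No power is claimed, so low power is not an error. All of this stands.

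A reader might infer that a p-value is the only juice-placebo result planned. Section 6.3 does not support that: it summarises change in each arm by means and standard deviations or medians and interquartile ranges, and a paired t-test already computes the mean difference and its standard error. What is missing is a reporting line, not an analysis.

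A reader might also go from 33 tests and 82% to the claim that preliminary efficacy will be called largely by chance. The documents do not support that either. The 24 correlations do not estimate a juice effect, Section 8.6 ties the term to no test, and the share of significant results due to chance depends on true effects that nobody knows.

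These arguments do not remove the wording of Section 6.3, which still uses 0.05 to settle significance for each outcome, with no interval for the difference.

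**Conclusion.** The concern holds in a limited form. At least nine juice-placebo comparisons are judged at unadjusted 0.05 with no interval planned for the difference. With all nulls true, the chance of at least one false positive is 26% for Aim 2 and 37% for all nine under independence, falling to about 17% and 21% at an assumed correlation of 0.7. Preliminary efficacy is undefined, so these figures measure the risk of a false lead and not the risk of a wrong decision about the next trial.

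The point about the correlations stands without any multiplicity argument. Within-arm correlations cannot link a juice-induced biomarker change to a juice-induced symptom change.

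The primary feasibility objective is unaffected. The changes are worth making because they are nearly free and fit the stated purpose.

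**What to change.** In Section 6.3:

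1. For every Aim 2 and exploratory outcome, report the juice-minus-placebo mean difference with 80% and 95% confidence intervals. Replace the significance sentence under both aims with a statement that p-values are descriptive.
2. Name total sleep time as the single efficacy read-out for the preliminary efficacy mentioned in Section 8.6, and call all other outcomes hypothesis-generating. If a test were kept for total sleep time alone, its false-positive risk would be 5%.
3. Replace or supplement the within-arm correlations with correlations of within-person juice-minus-placebo differences, after removing the period effect (for example by centring differences within sequence). Give intervals and label the results hypothesis-generating.

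No new data, visits or participants are needed. The trial gives up significance claims on many outcomes, and the difference correlations can use only participants with data from both periods. A Bonferroni correction is not recommended: at 0.05/9 = 0.0056 and n = 20, 80% power would need a difference of 0.90 SD, against 0.66 SD at 0.05.
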